## **6 STUDY INTERVENTION**

Study intervention is defined as any investigational intervention(s), marketed product(s) or placebo intended to be administered to or medical device(s) utilised by a study participant according to the study protocol.

### **6.1 Study Intervention(s) Administered**

#### **6.1.1 Investigational Products**

ASTRAZENECA AB will supply LLC AstraZeneca Pharmaceuticals AZD3152, solution for intramuscular injection, at a dosage of 150 mg / ml, 2 ml in a vial, as investigational drug in a standard package "IN BULK".

Further secondary packaging, labelling and release of IMP, will be carried out on territory of the Russian Federation by Manufacturing site and by Sponsor, in accordance with applicable regulations.

Placebo **CCI** [REDACTED]

Participants will be randomized to receive AZD3152 or placebo (3:1 ratio). There is no cap for randomization in each group to be implemented on site level of each investigational product, because it will increase coverage of IMP for trial conduction. Details of these study interventions are presented in [Table 5](#) and are described below.

Each vial of AZD3152 contains colourless to slightly yellow, clear to opalescent solution for injection. Label-claim volume per vial is 2 ml.

A placebo **CCI** [REDACTED] is colourless, clear solution for injection. **CCI** [REDACTED]

AZD3152 or placebo will be administered as a single IM injection in the anterolateral thigh.

If a participant experiences an immediate hypersensitivity reaction after receipt of the IM injection, appropriate necessary treatment should be prescribed. For details on the treatment of anaphylactic reactions after study intervention IM injections see [Appendix E](#).

Study intervention will be handled by an unblinded pharmacist (or designee, in accordance with local and institutional regulations) at the study site who will be independent of safety evaluations and other trial evaluations.

**Table 5 Investigational Products**

Intervention name	AZD3152	PLACEBO
Type	Drug	Placebo
Dose formulation	AZD3152 will be supplied as a single vial. AZD3152 vial contains 300 mg solution for injection. The solutions contain 150 mg/mL of AZD3152 in CCI [REDACTED]	Placebo is CCI [REDACTED] [REDACTED]
Unit dose strength(s)	300 mg AZD3152 at 150 mg/mL	CCI [REDACTED]
Dosage level(s)	300 mg single dose of AZD3152	single dose of 2 mL
Route of administration c	1 IM injection (thigh) of 2 mL of AZD3152	1 IM injection (thigh) of 2 mL of placebo
Use	Investigational	Placebo-comparator
IMP and NIMP	IMP	IMP
Sourcing	AstraZeneca	CCI [REDACTED]

Packaging and labelling	IMP will be provided in glass vials. Each glass vial will be labelled as per country requirement.	CCI [REDACTED]
--------------------------------	---	-------------------

IM = intramuscular; IMP = investigational medicinal product; NIMP = non-investigational medicinal product; w/v = weight per volume.

## 6.2 Preparation/Handling/Storage/Accountability

- IMP vials/ampoules are stored at 2°C to 8°C and must not be frozen.
- The Investigator, or an approved designated representative (eg, pharmacist), will ensure that all study intervention is stored in a secured area, in refrigerated temperatures (2°C to 8°C) and in accordance with applicable regulatory requirements.
- A temperature log will be used to monitor the storage conditions of IMP in the storage area. Temperature excursions outside the permissible range listed in the clinical supply packaging will be reported to the monitor upon detection. A calibrated temperature monitoring device will be used to record the temperature conditions in the drug storage facility or refrigerator. Storage conditions stated in the Investigator's Brochure may be superseded by the label storage.
- Study intervention must be kept in original packaging until the time of preparation to prevent prolonged light exposure.
- The Investigator or designee must confirm appropriate temperature conditions have been maintained during transit for all study intervention received and any discrepancies are reported. Use of study intervention for which a temperature deviation has been identified will not be permitted prior to AstraZeneca's notification.
- Only participants enrolled in the study may receive study intervention and only authorised site staff may supply or administer study intervention. All study intervention must be stored in a secure, environmentally controlled, and monitored (manual or automated) area in accordance with the labelled storage conditions with access limited to the Investigator and authorised site staff.
- The Investigator, institution, or the head of the medical institution (where applicable) is responsible for study intervention accountability, reconciliation, and record maintenance (ie, receipt, reconciliation, and final disposition records).

- Further guidance and information for the final disposition of unused study interventions, detailed dose preparation, handling, and administration information will be provided in the Investigational Product Handling Manual.

The doses of AZD3152 and placebo for administration must be prepared by the Unblinded staff members delegated by the Investigator (or an appropriate designee trained in study drug preparation), using aseptic technique and following local regulations and site requirements. Total time between retrieval of the drug from the vial/ampoule into the syringe and the start of administration must not exceed:

- 24 hours at 2°C to 8°C
- 4 hours at room temperature.

If the final product is stored at both refrigerated and ambient temperatures, the total time must not exceed 24 hours, otherwise a new dose must be prepared from new vials/ampoules (that is, the individual storage time limits are not additive). AZD3152 and placebo do not contain preservatives; any unused portion of the vial/ampoule must be discarded immediately after use.

## **6.3 Measures to Minimise Bias: Randomization and Blinding**

### **6.3.1 Randomization**

The participants will be randomized to receive AZD3152 or placebo (3:1 ratio).

All participants will be centrally assigned to randomized study intervention using an IWRS. Before the study is initiated, IWRS access and instruction will be provided to each site. Study intervention will be administered at the Visit 1.

The IWRS will provide to the Investigator(s) or pharmacists the kit identification number to be allocated to the participant at the dispensing visit. Routines for this will be described in the IWRS user manual that will be provided to each center.

### **6.3.2 Blinding**

Neither the participant nor any of the Investigators or Sponsor staff who are involved in the treatment or clinical evaluation and monitoring of the participants will be aware of the study intervention received. Since AZD3152 and placebo are visually distinct prior to dose preparation (due to differences in appearance), study intervention will be handled by an unblinded pharmacist (or designee, in accordance with local and institutional regulations) at the study site who will be independent of safety evaluations and other trial evaluations. Personnel preparing and administering study intervention may be the same individual. Syringe masking will be required in order to maintain the blind. The Investigator responsible for safety assessment will not attend the study intervention administration session but will be available in case of emergency (eg, anaphylactic shock).

The following personnel will have access to the randomization list during the study, prior to DBL:

- Those carrying out the packaging and labelling of IMP
- Those generating the randomization list and IWRs system
- The AstraZeneca Alliance Team members responsible for supply chain
- Unblinded AstraZeneca designees (if applicable)
- Unblinded pharmacist
- Staff of bioanalytic laboratory
- The unblinded team(s) (to be specified in the Study Integrity Plan) for interim analysis at AstraZeneca and/or its delegate.

The randomization code should not be broken except in medical emergencies when the appropriate management of the participant requires knowledge of the treatment randomization, or in the instance a participant wishes to be considered for a SARS-CoV-2 vaccine. The Investigator documents and reports the action to AstraZeneca, without revealing the treatment given to participant to the AstraZeneca staff.

AstraZeneca retains the right to break the code for SAEs that are unexpected and are suspected to be causally related to an IMP and that potentially require expedited reporting to regulatory authorities. Randomization codes will not be broken for the planned analyses of data until all decisions on the evaluability of the data from each individual participant have been made and documented.

### **6.3.3 Procedures for Unblinding**

The IWRs will be programmed with blind-breaking function. Unblinding should only occur within the IWRs system. In case of an emergency, in which the knowledge of the specific blinded study intervention will affect the immediate management of the participant's condition (eg, antidote available), the therapy can be unblinded by 41 authorized representatives of the study site. Participant safety must always be the first consideration in making such a determination. If a participant's intervention assignment is unblinded, the Sponsor must be notified within 24 hours after breaking the blind. The Investigator documents and reports the event to AstraZeneca, without revealing the treatment given to participant to the AstraZeneca staff.

## **6.4 Study Intervention Compliance**

When participants are dosed at the site, they will receive study intervention directly from the unblinded pharmacist or designee. The date, and time if applicable, of dose administered in the clinic will be recorded in the source documents and recorded in the eCRF.

## **6.5 Concomitant Therapy**

Any medication or vaccine (including COVID-19 vaccines and over-the-counter or prescription medicines) that the participant is receiving at the time of enrolment or receives during the study must be recorded on the Concomitant Medication eCRF along with:

- Reason for use

- Dates of administration including start and end dates
- Dosage information including dose and frequency

The Study Physician should be contacted if there are any questions regarding concomitant or prior therapy.

**Table 6** lists the permitted and restricted, medications during the study.

**Table 6 Permitted, Restricted, and Prohibited Medications**

Use Category	Type of medication/treatment	Timeline/instructions
Permitted	Routine vaccines except SARS-CoV-2 vaccines	All other vaccines except SARS-CoV-2 vaccines (see the 'Restricted' section below) are permitted; however, they should not be given within 14 days before or after administration of study intervention.
	Allergen immunotherapy	Allowed if participant has been receiving stable desensitization therapy for allergies for at least 30 days prior to screening and there is no anticipated change during the treatment period. Allergen immunotherapy should not be administered on the same day as study intervention. Non-prescription over-the-counter treatments for allergies such as antihistamines, decongestants, and nasal steroids are permitted for such participants.
	Commercial biologics, prednisone, immunosuppressive medications (eg, azathioprine, tacrolimus, cyclosporine, methotrexate, or cytotoxic chemotherapy)	Allowed. If possible, administration of biologics (eg, adalimumab) should be avoided on the same day as study intervention.
	Intravenous immunoglobulin infusion for participants with common variable immune deficiency	Allowed. If possible, administration of immunoglobulin should be avoided on the same day as study intervention.
	Participants may take concomitant medications prescribed by their healthcare provider for management of chronic medical conditions and/or for health maintenance. Healthcare provider or, where appropriate, Investigators should prescribe appropriate concomitant medications or treatments deemed necessary to provide full supportive care and comfort during the study. Participants who develop COVID-19 after receiving study intervention should be treated	

Use Category	Type of medication/treatment	Timeline/instructions
	according to local standard of care (which will be recorded as concomitant medication), including investigational agents outside a clinical trial setting.	
Prohibited	None	None
Restricted	Blood/plasma donation	Participants must abstain from donating blood or plasma from the time of informed consent and for 5 half-lives after study intervention administration, ie, 15 months.
	SARS-CoV-2 vaccines	SARS-CoV-2 vaccines should not be given within 6 months prior to Visit 1 (see Section 5). SARS-CoV-2 vaccines should also not be given during the study until after the Day 29 assessments.
	COVID-19 antivirals	COVID-19 antivirals for prophylaxis should not be given within at least 2 weeks prior to Visit 1 as well as during the study until after the Day 29 assessments. If the participant develops COVID-19, standard of care treatment is allowed.
	EVUSHIELD	EVUSHIELD should not be given within 6 months prior to Visit 1 and until 6 months after the dose of IMP.

SARS-CoV-2 = severe acute respiratory syndrome coronavirus 2

## **6.6 Dose Modification**

Dose modifications will not be permitted during the study.

## **6.7 Intervention After the End of the Study**

There is no intervention after the end of the study (see Section 4.4).

## **7 DISCONTINUATION OF STUDY INTERVENTION AND PARTICIPANT DISCONTINUATION/WITHDRAWAL**

### **7.1 Discontinuation of Study Intervention**

Each participant will receive a single dose of study intervention (AZD3152 or placebo). If a participant experiences an immediate hypersensitivity reaction after receipt of the IM injection, the participant should remain in the study to be evaluated.

Note that discontinuation from study intervention is NOT the same as a withdrawal from the study.

The study may be stopped if, in the judgment of AstraZeneca, trial participants are placed at

unnecessary risk because of clinically significant findings that:

1. meet individual stopping criteria or are otherwise considered significant
2. are assessed as causally related to study drug,
3. are not considered to be consistent with continuation of the study

Regardless of the reason for termination, all data available for the participants at the time of discontinuation of follow-up must be recorded in the eCRF. All reasons for discontinuation of treatment must be documented.

In terminating the study, the Sponsor will ensure that adequate consideration is given to the protection of the participants' interests.

See the SoA for data to be collected at the time of intervention discontinuation and follow-up and for any further evaluations that need to be completed (Section 1.3).

## 7.2 Participant Withdrawal from the Study

A participant may withdraw from the study at any time at his/her own request or may be withdrawn at any time at the discretion of the Investigator for safety, behavioral, compliance, or administrative reasons. This is expected to be uncommon.

A participant who considers withdrawing from the study must be informed by the Investigator about modified follow-up format (eg, telephone contact, a contact with a relative or treating physician, or information from medical records).

At the time of withdrawal from the study, if possible, an Early Study Intervention Discontinuation visit should be conducted, as shown in the SoA. See SoA for data to be collected at the time of study withdrawal and follow-up and for any further evaluations that need to be completed (Section 1.3).

A participant who considers withdrawing from the study should always be asked about the reasons and the presence of any AE. The investigator will follow up AEs outside of the clinical study.

If the participant withdraws consent for disclosure of future information, the Sponsor may retain and continue to use any data collected before such a withdrawal of consent.

If a participant withdraws from the study, it should be confirmed if he/she still agrees for existing samples to be used in line with the original consent. If he/she requests withdrawal of consent for use of samples, destruction of any samples taken and not tested should be carried out in line with what was stated in the informed consent and local regulation. The Investigator must document the decision on use of existing samples in the site study records and inform the Sponsor.

If the participant withdraws from the study, then his/her enrollment/randomization code cannot be reused. Withdrawal subjects will not be replaced.

If any of the stopping criteria detailed in Section 7.2.1 are met, prior approval of a substantial protocol amendment summarizing the emerging data and rationale for restart will be required to support study restart.

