#### **9.4.2 Endpoints**

##### **9.4.2.1 Primary Endpoint**

Primary safety endpoint includes AEs and SAEs, MAAEs, and AESIs collected throughout the study. Adverse events and SAEs will be coded using the most recent version of MedDRA and will be summarized by system organ class and preferred term and by severity and relationship to study intervention as judged by the Investigator.

Intercurrent events: treatment policy will be applied, i.e., all events collected will be included in the analysis.

Safety analysis set will be used for the analysis of this endpoint.

Number and proportion of participants with AEs, SAEs, MAAEs, and AESIs (occurring throughout the study period after study intervention administration) separately will be provided for each arm, and will be descriptively compared between arms.

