3.3.1 General Study Level Definitions

The study will consist of 2 periods: a screening period of up to 7 days (Day -7 through Day -1), and a treatment and follow-up period lasting 6 months after the administration of study intervention which consist of Visit 1 (Day 1), Visit 2 (Day 8), Visit 3 (Day 15), Visit 4 (Day 29), Visit 5 (Day 91) and Visit 6 (Day 181). Acceptable visit windows presented in Section 3.3.2. More detailed description of study visits and procedures presented in the Schedule of Activities (Table 1) of the CSP.

Categorical variables will be summarized using frequency, percentages (where the denominator for calculation is the underlying analysis set population, unless otherwise stated).

Continuous (quantitative) data will be presented as:

- Number of valid observations (n);
- Arithmetic Mean (M) or Geometrics Mean (gM) if appropriate;

- Standard deviation (SD) or Geometric standard deviation (gSD) if appropriate;
- 95% confidence interval (CI) if appropriate;
- Minimum value (Min.);
- Maximum value (Max.);
- Median (Me);

Data after log transformation will be rounded up to 3 decimals.

For continuous data, descriptive statistics will be rounded according to rules:

Mean, geometric mean, median and quartiles will be represented with an accuracy of 1 decimal place greater than the measured values. Standard deviation and geometric standard deviation will be represented with an accuracy of 2 decimal places greater. Minimum and maximum will have the accuracy of the measured values.

For categorical data, percentages will be rounded to 1 decimal place.

Data will be provided in data listings sorted by treatment arm and participant number. Tabular summaries will be presented by the actual treatment received for safety analysis and by the assigned for efficacy analysis.

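### Investigator-initiated withdrawal after the single dose ends safety observation while the participant stays in the denominator, so later events can be missing from the primary safety proportions

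*Protocol*

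**What the plan says.** Protocol Section 7.1 provides for a single dose per participant. Under Section 7.2 a participant "may be withdrawn at any time at the discretion of the Investigator for safety, behavioral, compliance, or administrative reasons", with the comment "This is expected to be uncommon". A participant who considers withdrawing "must be informed by the Investigator about modified follow-up format" (telephone, a relative or treating physician, medical records). That participant is also to be asked about reasons and any AE, after which the section says "The investigator will follow up AEs outside of the clinical study". An early discontinuation visit is to be held where possible.

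Section 8.3.1 collects AEs, MAAEs and AESIs from dosing, and SAEs from consent, up to the last visit. Section 8.3.2 says that AEs unresolved at the last assessment are followed without further eCRF entry.

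The primary endpoint is the occurrence of AEs, SAEs, MAAEs and AESIs throughout the study. For intercurrent events, Section 9.4.2.1 says "treatment policy will be applied, i.e., all events collected will be included in the analysis". SAP Section 3.3.1 calculates percentages "where the denominator for calculation is the underlying analysis set population" unless otherwise stated. SAP Section 4.2.1.3 reports the number and percentage of participants with at least one event, and the number of events. SAP Appendix B generally does not impute missing safety data.

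**The concern.** With repeated dosing, withdrawal for safety may at least accompany the end of exposure. Here exposure is complete on Day 1 and the antibody is designed to persist for months. Taking a dosed participant out of the study therefore removes only the record of what happens next. When the reason is safety, or compliance in a participant who is becoming unwell, the loss of follow-up may be related to the outcome.

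The treatment-policy strategy does not help, because it includes events that were collected and cannot recover events that were not. The denominator does not shrink when observation stops, so a withdrawn participant contributes a non-event to every category in which nothing was recorded beforehand. At stake is the accuracy of the primary safety proportions, above all for SAEs and AESIs. Protocol Section 9.2 describes these as infrequent in the reference study, so single participants matter.

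**Working it through.** **1. The plan's own numbers.** Protocol Section 9.2 needs at least 108 participants at 3:1 (81 + 27), expects about 5% drop-out and randomizes 116. Check: 108 / 0.95 = 113.7, so 114. Rounded up to a multiple of 4 for the 3:1 ratio, this is 116, or 87 + 29. The figure reproduces.

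**2. Is the detection probability at risk?** The plan uses 1 − (1 − p)^n with 80% power. The threshold p is redacted. Solving for 81 participants gives p = 1 − 0.2^(1/81) = 1.97%, so p = 2% is assumed here.

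| AZD3152 participants followed | 1 − 0.98^n |
|---|---|
| 87 (all) | 82.8% |
| 83 (4 give no data) | 81.3% |
| 81 (6 give no data) | 80.5% |

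The planned drop-out allowance already covers this. The issue is bias in the reported proportions and not power.

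**3. What can be lost, by category.**

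| Situation at withdrawal | Effect on the primary summary |
|---|---|
| AE that caused withdrawal | Recorded (an AE variable in Section 8.3.2 asks for it); counts as an AE, and as SAE, MAAE or AESI if it qualifies |
| Other AEs before withdrawal | Recorded; count |
| Later event in a category or preferred term with nothing recorded earlier | Not systematically collected; participant counts as a non-event there |

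**4. Size per participant.** The denominator is fixed, so each missed participant lowers a proportion by 1/N:
- AZD3152: 1/87 = 1.149%, or 1.1 points.
- Placebo: 1/29 = 3.448%, or 3.4 points.

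**5. Bounds at the planned drop-out.** 5% × 87 = 4.35 and 5% × 29 = 1.45, so about 4 and 1 participants. The 5% covers drop-out for every reason, so treating all of it as Investigator-initiated is an upper assumption.
- AZD3152, all 4 with a later uncounted event: 4/87 = 4.6 points.
- AZD3152, 10% to 50% of the 4 (assumed): 0.4/87 = 0.5 points to 2/87 = 2.3 points.
- Placebo, 1 participant: at most 3.4 points.

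**6. Comparison: withdrawal unrelated to risk.** Assume a constant hazard and a uniform withdrawal time. With true proportion P and h = −ln(1 − P), a withdrawn participant has an event recorded with mean probability 1 − P/h.
- P = 35% (assumed): h = 0.431 and 1 − 0.35/0.431 = 0.188. Observed proportion: 0.95 × 0.35 + 0.05 × 0.188 = 34.2%.
- P = 2% (assumed): observed proportion 1.95%.

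Uninformative withdrawal at 5% is therefore nearly harmless. A material bias needs withdrawal that is related to later risk.

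**7. Does the SAP correct for it?** The SAP specifies no exposure-adjusted incidence, no time-to-event analysis of AEs and no sensitivity analysis for early withdrawals. SAP Section 4.1.3.1 lists as an important deviation a participant who meets study-withdrawal criteria but is not withdrawn, although the protocol sets out no list of individual criteria. If anything, that entry favours withdrawal.

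**The case against.** The documents limit the loss in several ways. The early discontinuation visit assesses AEs, SAEs, MAAEs and AESIs (Protocol Table 1). Late events with suspected causality that the Investigator learns of are reported to the Sponsor within 24 hours (Section 8.3.1). Vital status is sought under Section 7.3. The SAP tabulates reasons for withdrawal (4.1.1) and follow-up duration by arm (4.3.1.2), so an imbalance would be visible. Nothing is tested, so no error rate is affected. The sentence on follow-up outside the study comes just after one about a participant who considers withdrawing, and may refer only to AEs already present.

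These safeguards are real but partial. The discontinuation visit is a single contact, held where possible. Late reporting depends on suspected causality, whereas the endpoint does not, and entry into the analysis is not stated. Vital status identifies deaths only. Tabulating follow-up shows an imbalance without correcting it. If the sentence on outside follow-up is read narrowly, the protocol still provides no collection of new events after an Investigator-initiated withdrawal, because the modified format is worded only for a participant who considers withdrawing.

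Three stronger readings are tempting, and the documents do not support them:
- *Withdrawn participants are counted as event-free.* This is so only for categories or terms with no earlier event. Someone withdrawn because of an AE already counts as having one.
- *Sections 7.1 and 7.2 contradict each other.* Section 7.1 says that after an immediate hypersensitivity reaction "the participant should remain in the study to be evaluated". That is a specific rule and Section 7.2 a general permission; both can be followed.
- *A serious event will probably be missed.* Any such probability needs the number of Investigator-initiated withdrawals and their later risk. The plan gives neither, and Section 9.2 describes SAE and AESI frequencies as low.

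**Conclusion.** The concern holds as a risk of bias in the primary safety proportions. After a single dose, Investigator-initiated withdrawal ends observation only, and the analysis has no means of allowing for what is then not seen. The direction is downward, for SAE, MAAE and AESI proportions and for individual preferred terms not recorded before withdrawal. For a participant withdrawn with no AE so far, it extends to the overall AE proportion. The loss may differ between arms, but the documents do not show that it will.

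The firm figures are 1.1 points per missed participant in the AZD3152 arm and 3.4 in the placebo arm. The bound of 4.6 points for AZD3152 requires all four planned drop-outs to be Investigator-initiated and all four to have a later uncounted event, which is an extreme assumption. Detection probability stays above the planned 80% at 5% drop-out, given p = 2%. Selective loss is possible but not established, because the number, reasons and arm balance of such withdrawals are not given. This is a worthwhile low-cost improvement, and it does not invalidate the design.

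**What to change.** **Protocol Section 7.2.** State that, after dosing and unless the participant withdraws consent, AE, SAE, MAAE, AESI and COVID-19 data continue to be collected and entered in the eCRF to Day 181 by the modified follow-up format already described. Say explicitly that this applies to Investigator-initiated withdrawal. Align the sentence on follow-up outside the study, and Section 8.3.2, with this.

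**SAP Section 4.2.1.** State that events learned through this route enter the treatment-policy analysis. An exposure-adjusted incidence or a sensitivity analysis for early withdrawals would be a useful addition.

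**Cost.** An amendment to the wording, a few additional telephone contacts and some eCRF entry. Weekly remote contacts are already in the schedule, and no extra participants or procedures are needed. The Investigator's discretion over visits and clinical care is unchanged.
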